**Does Vitamin C Reduce Finger Stiffness after
Distal Radius Fractures: a Placebo Randomized
Controlled Trial.**

NCT02216812

**Version Date of the Document: 22 February
2017**

PARNTERS HUMAN RESEARCH
DETAILED PROTOCOL

Does Vitamin C Reduce Finger Stiffness after Distal Radius Fractures: a Placebo Randomized Controlled Trial.

Version 4
2-22-2017

BACKGROUND & SIGNIFICANCE

The reported prevalence of disproportionate pain and disability among patients recovering from a fracture of the distal radius varies widely, between 1% and 37% in published series,¹⁻⁷ perhaps in part because it is poorly defined, known by so many different names, subjective, and unverifiable. In general, physicians ascribe disproportionate pain and disability to a poorly understood pathophysiologic process currently labeled “complex regional pain syndrome”, while psychologists understand this as ineffective coping strategies.⁸ Studies consistently identify psychological factors (catastrophic thinking in particular) as the most important determinants of pain intensity, finger stiffness, and magnitude of disability after distal radius fractures.^{8,9}

Along these lines, it is difficult to interpret the trials suggesting that vitamin C limits the occurrence of complex regional pain syndrome, given that the diagnosis is subjective and variably defined, and the only published trials were performed by advocates of vitamin C.^{6,10} We see this reflected in clinical practice, as only 11% of the orthopaedic surgeons always prescribes vitamin C after a distal radius fracture, making it one of the least adhered to recommendations of the AAOS clinical practice guidelines.¹¹ In addition, there is a lack of clarity regarding the mechanism by which vitamin C would decrease the incidence of complex regional pain syndrome.¹² We are interested in the effect of vitamin C after distal radius fractures on objective measurement of finger motion, patient reported outcome measures, and pain intensity, instead of the previously used, subjective and imprecise Veldman criteria for complex regional pain syndrome¹³, i.e., (i) unexplained diffuse pain, or (ii) edema, (iii) difference in skin color, or (iv) temperature, or (v) limited active range of motion.

SPECIFIC AIMS

Primary null hypothesis

There is no difference in finger stiffness (distance to palmar crease) between patients taking vitamin C or placebo after six weeks after a distal radius fracture.

Secondary null hypotheses

There is no difference in PROMIS upper extremity function and pain score between patients taking vitamin C or placebo after a distal radius fracture.

There are no factors associated with finger stiffness, PROMIS upper extremity function, and pain intensity after fracture of the distal radius.

SUBJECT SELECTION

Patients will be enrolled in the outpatient clinic at the Hand & Trauma Services at Massachusetts General Hospital.

Inclusion Criteria:

- All adult (age 18 or greater) patients presenting to the Hand and Orthopaedic Trauma Services of the Massachusetts General Hospital (MGH) within two weeks of a fracture of the distal radius, either operatively or nonoperatively treated.

Exclusion criteria:

- Patients with severe kidney failure or kidney stones, known allergy for vitamin C or pregnancy, or patients who are not fluent in either English or Spanish.
- Wrist fracture within the last year on the newly fractured side
- Confounders (baseline characteristics): fracture on the dominant side, current vitamin C supplements.

SUBJECT ENROLLMENT

The treating surgeon at the Hand or Orthopedic Trauma service will determine if the patient is eligible to participate in the study. The surgeon will introduce the study to the patient and answer any questions that the patient may have about the study or about randomization. If the patient agrees to participate, a trained research coordinator (pre-med student) or trained research assistant (PhD or medical student) not involved in clinical care, will obtain consent and begin enrollment procedures. As with the other research studies in this department, there will be no coercion. The research coordinator or research assistant will explain to the patient that participation in this study is completely voluntary and that the patient may withdraw at any time. The research coordinator or research assistant will offer all subjects the opportunity to speak with a licensed physician Investigator during the consent process.

Subjects will be given a copy of the informed consent form, and be informed that their participation is voluntary and that they can withdraw at any time during the study. Subjects make take as long as they like to consider participation, provided they still meet all enrollment criteria.

Study staff will provide the patient with a box of medication, containing either vitamin C or placebo (both completely similar in appearance, taste and smell). The pharmacist involved in preparing the placebo will randomize the boxes of medication according to a list of generated random numbers (Stata 13). The

pharmacist will be the only person with access to the code until conclusion of the trial.

STUDY PROCEDURES

Eligible patient, after informed consent, will be randomly assigned, double-blind, to take either placebo or vitamin C 500 mg for 6 weeks.

At enrollment and 6 weeks (5-8 weeks acceptable) after fracture we will measure: DPC (dig II-V), PROMIS UE CAT, PROMIS pain interference and VAS score; all questionnaires will be filled out in REDCap. If the researcher misses the subject at the 6 week follow-up or if their appointment is outside of the 5-8 week timeframe, three attempts will be made to contact each patient via email and via telephone to complete the 6 week follow-up questionnaires. To address, one of the secondary hypotheses, patients will be contacted 6 months after injury by email; unresponsive patients will be contacted by telephone to assist them with filling out the questionnaires. Three attempts will be made to contact each patient via email and via telephone to complete the follow-up.

Measured variables

At enrollment and 6 weeks (5 to 8 weeks acceptable) after fracture:

- Finger tip distance to palmar crease of fingers II-V (DPC)
- PROMIS Upper Extremity Function (Short form)
- PROMIS Pain Interference Short form
- 0-10 ordinal rating of pain intensity

At 6 months (5 to 8 months acceptable) after fracture:

- PROMIS UE – Short form
- 0-10 ordinal rating of pain intensity

BIOSTATISTICAL ANALYSES

Difference in DPC, function, pain interference and pain will be assessed by Wilcoxon-Mann-Whitney test.

Assuming an effect size of similar magnitude to previous studies¹⁰, power analysis suggests 134 patients provide 80% power to detect a difference with an alpha of 0.05 (effect size 0.50, two tailed Wilcoxon-Mann-Whitney test). As trauma patients are notoriously hard to track, halfway through the study we will assess enrollment and adjust sample size accordingly to account for lost to follow-up.

RISKS AND DISCOMFORTS

Although controversy exists regarding the value of prescribing vitamin C to patients with distal radius fractures, there appears to be limited downside with its use.

Adverse effects of vitamin C are dose-dependent and occur at doses well above the recommended daily dose of 60 mg. Generally, adverse side effects can be avoided with doses below 1000 mg daily in healthy people.¹⁴ In this study, patients who receive the vitamin C treatment will only take 500 mg daily. When several grams of vitamin C are taken at once, diarrhea and abdominal bloating are the most frequent side effects. In addition, renal calculi can precipitate as a result of the ingestion of excess vitamin C. Oxalic acid is produced and renally excreted during vitamin C metabolism. In patients with underlying hyperoxaluria, oxalate excretion is accelerated with vitamin C doses above 1000 mg daily and can contribute to formation of renal calculi. Similarly, hyperuricosuria can occur with large doses of vitamin C, also leading to formation of renal calculi. In patients requiring dialysis, hyperoxalemia can occur with doses as low as 500 mg daily. Therefore, these patients are excluded from our study.

The subject will be inconvenienced by having to complete study related questionnaires and physical examination (about 20 minutes).

POTENTIAL BENEFIT

There may or may not be any direct benefits to the individual subjects. Subjects may benefit from the Vitamin C treatment by experiencing reduced pain and reduced finger stiffness. It is also possible that the subjects will not directly benefit from the treatment, and will recover from their injury as they would under the standard of care treatment outside of this research. Either outcome will contribute to the understanding of the role of vitamin C in the healing of distal radius fractures.

MONITORING AND QUALITY ASSURANCE

Any adverse events will be recorded by a full time research coordinator involved in this project and discussed with the PI immediately. An overview of all adverse events will be discussed at the monthly research meeting at which the PI will decide whether to continue or alter/stop the trial.

The PI will have overall responsibility for the conduct and monitoring of the study and safety of subjects. The research coordinator has an assistive role and will monitor outcomes on a daily basis. The research coordinator will have an assistive role and will be responsible for monitoring outcomes on a daily basis and the research coordinator will discuss all outcomes with the PI on a monthly basis at the research meeting. No independent monitoring will occur. All investigators and study staff will be responsible for reporting adverse effects to the research coordinator. Should any adverse events occur, the research coordinator will report such events to the PI immediately. The research coordinator will report adverse events to the IRB in accordance with the IRB adverse event reporting procedures.

There will be a full-time research coordinator responsible for adherence to all IRB rules and guidelines and for the accuracy and completeness of all forms, entries, and

informed consent. The research coordinator is responsible for monitoring all data and adherence to the IRB-approved protocol on a daily basis, and all data and study details will be reviewed with the PI at the monthly research meeting. The research coordinator will report any deviations from the protocol to the PI immediately.

All data from subjects will be filed in locked cabinets in the research office in individualized research folders, independent of clinical charts or any other medical record in electronic format. Any magnetic or electronic information will be saved in password-protected computers to which only research coordinator and persons involved with the research project will have access.

All participants are given a participation number/code at the time of enrollment matching with their received medication box. This code is kept on all data sheets instead of the patient name. Subject information is only accessible by Partners authorized investigators and will not be shared with outside entities. The final results after statistical analysis will not be shared with the any institution.

REFERENCES

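### Operated and nonoperated fractures are pooled with treatment neither listed as a variable nor used in the analysis: the comparison stays valid but may lose some precision

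*Combined protocol and SAP*

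**What the plan says.** - **Population.** The inclusion criterion under Subject Selection takes adults presenting "within two weeks of a fracture of the distal radius, either operatively or nonoperatively treated". The two-week limit applies to presentation. No passage dates or limits surgery.
- **Randomisation.** Under Subject Enrollment, the pharmacist "will randomize the boxes of medication according to a list of generated random numbers (Stata 13"). No stratum, block or allocation ratio is stated.
- **Primary question.** Specific Aims: "There is no difference in finger stiffness (distance to palmar crease) between patients taking vitamin C or placebo after six weeks" after the fracture.
- **Timing.** Measured variables: "At enrollment and 6 weeks (5 to 8 weeks acceptable) after fracture", for all patients.
- **Analysis.** Biostatistical Analyses: "Difference in DPC, function, pain interference and pain will be assessed by Wilcoxon-Mann-Whitney test". No covariate or stratum is named.
- **Size.** "134 patients provide 80% power to detect a difference with an alpha of 0.05" ("effect size 0.50, two tailed Wilcoxon-Mann-Whitney test").
- **Variables.** The measured-variables list holds DPC, the two PROMIS scores and a pain rating. The exclusion criteria name two baseline confounders, dominant-side fracture and current vitamin C supplements. Treatment type and surgery date are in neither list.
- **Secondary aim.** One secondary hypothesis concerns factors associated with stiffness, function and pain. No factor list or model is given.

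**The concern.** The inclusion criterion itself separates two kinds of patient whose finger motion may follow different courses, and the plan then does nothing with that split. If the two groups differ in DPC, the difference adds to the spread against which the vitamin C effect is judged. A chance excess of operated patients in one arm would also move that arm's DPC for reasons unrelated to vitamin C. A reader of the results would want to see that mix, and the listed variables would not show it. The secondary aim on factors associated with stiffness would also lack an obvious candidate. The design has little room to give precision away: 134 patients only just reach 80% power, and the plan itself expects trouble with follow-up.

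**Working it through.** **Inputs from the documents.** N = 134, power 80%, two-sided alpha 0.05, effect size 0.50, Wilcoxon-Mann-Whitney test, DPC window of 5-8 weeks after fracture.

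**Assumptions, because the documents are silent.** Allocation 67:67; operated share p; gap g in DPC between operated and nonoperated patients, in within-group SDs; normal outcome in the simulations.

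**1. The plan's own figure.** A two-sample t-test at d = 0.50 needs 63.77 per arm. Dividing by the Wilcoxon efficiency 3/π = 0.955 gives 66.78, so 67 per arm and 134 in total. Power at 67 per arm is 80.1%. The stated figure reproduces.

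**2. Chance imbalance.** With K operated patients among 134 and no strata, the number X in one arm is hypergeometric (134, K, 67). The between-arm gap in operated share is (2X − K)/67, with SD = 2·√(p(1−p)/133).
- Half operated (K = 67): SD = 2·√(0.25/133) = 8.7 points; P(gap ≥ 10 points) = 30%; P(gap ≥ 20 points) = 1.5%.
- 30% operated (K = 40, p = 40/134): SD = 2·√(0.209/133) = 7.9 points; P(gap ≥ 10 points) = 19%.

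Gaps move in steps of 2/67 = 3.0 points. The smallest gap that qualifies is 7/67 = 10.4 points when K = 67 and 8/67 = 11.9 points when K = 40. This is why 35% operated (K = 47, smallest gap again 7/67) gives 28%, well above the 19%.

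**3. What an imbalance does to the arm difference.** Shift = gap in share × g. A 10-point gap moves the difference by 0.03, 0.05 or 0.10 SD for g = 0.3, 0.5 or 1.0, against a planned 0.50. The median absolute gap at half operated is about 0.674 × 8.7 = 5.9 points, a shift of 0.02 to 0.06 SD over the same range.

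**4. Validity.** If vitamin C has no effect, every allocation from the list is equally likely whatever the treatment mix, so the rank test keeps its level. Simulated type I error of the unstratified test (6,000 runs per scenario, p = 35-50%, g = 0 to 1.0) was 4.8-5.8%, with no trend in g.

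**5. Precision.** Treatment type carries p(1−p)g²/(1 + p(1−p)g²) of the DPC variance. At p = 0.5 this is 2.2%, 5.9% and 20% for g = 0.3, 0.5 and 1.0.

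Simulated gain in power from van Elteren over the unstratified test (10,000 runs, 134 patients, 0.50 read as total-SD units, unstratified power near 80% throughout):

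| g | Gain, half operated | Gain, 30% operated | Power with van Elteren |
|---|---|---|---|
| 0.3 | 0.4 points | 0.0 points | about 80% |
| 0.5 | 1.7 points | 0.9 points | 81-82% |
| 1.0 | 7.9 points | 6.5 points | 86-88% |

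Hand check at g = 1.0, p = 0.5: in within-group units the effect is 0.50 × √1.25 = 0.559. With 67 × 0.955 = 64 effective patients per arm, z = 0.559 × √(64/2) − 1.96 = 1.20, or about 88%.

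If 0.50 is instead in within-group SD units, the planned test has about 77-78% power at g = 0.5 and 69-72% at g = 1.0 (p = 35-50%). Stratifying brings it back to about 79-80%.

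**6. Time since surgery at the primary measurement.** This is 5 to 8 weeks minus the week of surgery: week 0 gives 5-8, week 1 gives 4-7, week 2 gives 3-6. If surgery falls on days 0-14, the range is 3-8 weeks. Surgery at week 3 would give 2-5. The documents fix only presentation, not surgery, so 3-8 is conditional.

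**The case against.** The strongest reply is that nothing here is an error. Randomisation makes any imbalance random, and the Wilcoxon p-value already allows for it. A reader might infer that pooling biases the vitamin C comparison; it does not, and that part of the reply stands in full.

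A reader might also infer that the single clock from fracture is a flaw, or take 3 to 8 weeks after surgery as a fact of the design. The clock matches the primary hypothesis, which is framed from the fracture. The 3-8 range depends on a surgery date that the documents never give. Part of that spread is also the 5-8 week window, which applies to every patient. Stratifying by treatment leaves the clock unchanged.

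Nor do the documents show that an imbalance could never be examined. Treatment and surgery date can probably be taken from the chart. The measured-variables list is also not a full baseline list, since the two named confounders are missing from it too. Likewise, that the box list is unstratified is read from silence.

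Finally, the Background ranks psychological factors, not operative treatment, as the main determinants of stiffness, and no document gives a DPC gap between the groups. This limits how large a benefit can be claimed. It does not remove the point: the entry criterion names the split, the stated test ignores it, and no listed variable captures it. Chart data help only if the plan says they will be extracted and how they will be used.

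**Conclusion.** The point holds as a modest improvement in precision and interpretability, not as an error in the plan. Treatment type is part of the entry criterion but absent from the listed variables and from the stated analysis. An imbalance of 10 points or more in operated share is fairly common at this size (about 19% to 30% for 30% to 50% operated), but its effect is small beside 0.50: at most 0.10 SD per 10 points over the gaps considered. The power gain from stratifying is negligible at a 0.3 SD gap, 1-2 points at 0.5 SD and about 6-8 points at 1.0 SD. These sizes rest on assumed operated shares, assumed gaps, 1:1 allocation, a normal outcome and the total-SD reading of the effect size.

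**What to change.** 1. Record two fields, in REDCap or from the chart: treatment at enrollment (operative done or planned, versus nonoperative) and date of any surgery.
2. Prespecify, before unblinding, a Wilcoxon test stratified by treatment status at enrollment (van Elteren) as the primary DPC comparison. Keep each patient in the enrollment stratum, so that the stratum cannot depend on anything that happens after allocation.
3. Report the operated share by arm, and describe time from surgery to the DPC measurement. Surgery date does not enter the primary test.
4. If boxes are not yet randomised, also generate a separate blocked list and box series for each stratum. If they are, keep the existing list; the stratified analysis alone recovers most of the precision.

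The cost is two data fields, and a second box series only if step 4 applies. Patients classed nonoperative who are operated on later stay in their enrollment stratum, which slightly dilutes the gain. The sample size stays at 134 and no clinical care changes.

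### Does timing DPC from fracture, while the six-week course starts after consent, leave the primary result uninterpretable?

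*Combined protocol and SAP*

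**What the plan says.** Two clocks run in the combined protocol and SAP.

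- **Outcome clock.** Study Procedures states "At enrollment and 6 weeks (5-8 weeks acceptable) after fracture we will measure" DPC, among other variables. The primary null hypothesis in Specific Aims uses the same origin, comparing finger stiffness "between patients taking vitamin C or placebo after six weeks after a distal radius fracture".
- **Treatment clock.** Study Procedures assigns patients, once they have consented, "to take either placebo or vitamin C 500 mg for 6 weeks". The inclusion criterion covers adults presenting "within two weeks of a fracture of the distal radius, either operatively or nonoperatively treated". Subject Enrollment sets no fixed limit on deciding: "Subjects make take as long as they like to consider participation, provided they still meet all enrollment criteria".

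On intake, Risks and Discomforts says "In this study, patients who receive the vitamin C treatment will only take 500 mg daily". Monitoring and Quality Assurance says "The research coordinator is responsible for monitoring all data and adherence to the IRB-approved protocol on a daily basis" and has the coordinator report protocol deviations to the principal investigator. The measured-variables list names DPC, two PROMIS scores and pain intensity. It names no first-dose date, pill count or intake question, and Biostatistical Analyses has no exposure summary.

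**The concern.** The course and the assessment are both called six weeks but start on different days. A patient who consents late and is seen early may be only halfway through the course when DPC is measured. One who starts on the day of fracture and is seen at eight weeks has been off treatment for two weeks. The primary analysis pools them.

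At stake is the reading of the result, above all a null one. If the report called it the effect of six weeks of vitamin C, that would be inaccurate for many patients. Without a first-dose date or intake record, a reader could not separate a treatment that does not work from one that was incomplete or not taken. Intake cannot be reliably reconstructed after the trial.

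**Working it through.** **The plan's own figure.** Inputs from Biostatistical Analyses: effect size 0.50, two-sided alpha 0.05, power 80%, Wilcoxon-Mann-Whitney test; 1:1 allocation is assumed. A two-sample t-test needs 63.77 per arm. Dividing by the Wilcoxon efficiency under normality, 3/π = 0.955, gives 66.8, rounded up to 67 per arm and 134 in total, with power 80.1%. The stated 134 reproduces. Time on treatment is not an input to it.

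**Elapsed course days at DPC.** Inputs: visit on day 35 to 56 after fracture (5 to 8 weeks), course of 42 days (6 weeks), first dose on day 0 to 14. The last input is an assumption, because the two-week limit is on presentation.

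Elapsed course days = min(42, visit day − first-dose day). Days since the end of the course = max(0, visit day − first-dose day − 42).

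| Visit day | First dose day 0 | First dose day 7 | First dose day 14 |
|---|---|---|---|
| 35 | 35 | 28 | 21 |
| 42 | 42 | 35 | 28 |
| 56 | 42 (ended 14 days before) | 42 (ended 7 days before) | 42 (ends that day) |

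So the range is 21 to 42 days over the window and 28 to 42 at day 42. DPC falls between 21 days before the end of the course (35 − 56) and 14 days after it (56 − 42). Each day of delay in the first dose beyond day 14 lowers the floor by one day. Counting doses instead of elapsed days shifts the boundary by one: with daily intake from day 0, the 42nd dose falls on day 41. These are days available for treatment; actual intake may be lower. The documents give no distribution of start or visit days, so the share of patients who have completed the course cannot be estimated.

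**Consequences, taken in turn.**

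1. *Bias.* The entry rule, course length and visit window are the same in both arms, and patients and staff are blinded. Start and visit days have no reason to differ by arm. The windows themselves create no difference between arms, and if vitamin C has no effect, the Wilcoxon test keeps its error rate whatever the spread in exposure.
2. *Consistency.* Hypothesis and measurement are both timed from fracture, so the analysis answers the question asked.
3. *Power.* The effect size is borrowed from an earlier trial. The documents do not say how much treatment those patients had received when assessed, nor how the effect depends on duration. No dilution can be calculated.
4. *Description.* The entry rule needs a fracture date and the window needs a visit date. Staff hand over the medication box, and the code matching it is assigned at enrollment. Days from enrollment to DPC can therefore be tabulated by arm with what the plan already requires, as an upper limit on time on treatment.

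**The case for a change.** The strongest case for a change is that the remedy is cheap and the information perishable. Two form items, one sentence defining the effect and one descriptive table would let the report say how much of the course had been taken, without touching visits, sample size or test. The protocol treats current vitamin C supplements as a baseline confounder, yet lists no record of vitamin C intake during treatment. Protocol monitoring without an intake item could miss a stopped course.

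Part of this stands. Actual first-dose date and intake are not listed, and recording them would be good practice. Three things weaken it.

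- The variables list covers outcomes and is not exhaustive. It also omits hand dominance, baseline supplement use and adverse events, all of which the protocol mentions elsewhere. Absence from it is weak evidence that an item will not be collected, and deviation reporting is a route by which missed treatment could be recorded.
- The sentence in Potential Benefit that "Either outcome will contribute to the understanding of the role of vitamin C in the healing of distal radius fractures" follows two sentences contrasting subjects who benefit with subjects who do not. It most naturally refers to them, and is poor support for a claim that the protocol promises an informative null trial.
- No section says the result will be presented as the effect of a completed six-week course. The misreporting is hypothetical.

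**Conclusion.** No change to the plan follows. The two clocks do differ: nominal time on treatment at DPC runs from 21 to 42 days if the first dose is taken by day 14, and lower if it is later. The randomized comparison remains unbiased, the hypothesis and measurement agree, and 134 patients is unaffected. Collecting first-dose date and intake would add description but would alter neither the primary test nor its conclusion.

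This rests on two assumptions: that start and visit days are handled alike in both arms, as blinding and common windows imply, and that the report describes the result as the effect of assignment on DPC at six (5 to 8) weeks after fracture. A competent analyst would do that from the hypothesis as written. Recording first-dose date and intake is a reasonable minor suggestion for the case report form.

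### Does naming the upper extremity function instrument as CAT in one place and short form in another leave a secondary outcome undefined?

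*Combined protocol and SAP*

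**What the plan says.** Study Procedures summarises the visits in one sentence: "At enrollment and 6 weeks (5-8 weeks acceptable) after fracture we will measure: DPC (dig II-V), PROMIS UE CAT". The sentence goes on: "PROMIS pain interference and VAS score; all questionnaires will be filled out in REDCap".

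The Measured variables list covers the same visits under the heading "At enrollment and 6 weeks (5 to 8 weeks acceptable) after fracture". Its function entry is "PROMIS Upper Extremity Function (Short form", and its pain entry is "0-10 ordinal rating of pain intensity". For 6 months the list gives "PROMIS UE – Short form" as the only function measure.

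Function appears in both of the secondary hypotheses. One of them reads "There is no difference in PROMIS upper extremity function and pain score between patients taking vitamin C or placebo after a distal radius fracture"; the other, on prognostic factors, reads "There are no factors associated with finger stiffness, PROMIS upper extremity function, and pain intensity after fracture of the distal radius". Neither names a form. Biostatistical Analyses says only that function is among the outcomes compared by the Wilcoxon-Mann-Whitney test.

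**The concern.** An adaptive test (CAT) and a fixed short form are two ways of administering one measure, and a protocol should name one of them for each visit. Here two current statements about the same visits disagree. Nothing gives one section precedence, says that both forms are given, or says that one replaces the other. The hypotheses and the analysis sentence fit either form, so they do not settle it.

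Three things could be at stake.

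- A tested secondary outcome might have two candidate scores and no rule for choosing between them.
- If Study Procedures governs, the form would change between 6 weeks and 6 months without comment.
- The research coordinator, who checks adherence daily under Monitoring and Quality Assurance, would find that giving either form alone departs from one of the two statements. That section provides for no independent monitor to notice.

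**Working it through.** The core of this check is a comparison of texts. Study Procedures and the Measured variables list give the following.

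| Time point | Study Procedures | Measured variables |
|---|---|---|
| Enrollment | CAT | Short form |
| 6 weeks | CAT | Short form |
| 6 months | Questionnaires, no form named | Short form |

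**Extent of the conflict.** Four measures are listed at enrollment and 6 weeks: finger stiffness, function, pain interference and pain intensity. Only function conflicts, so 1 of 4. Pain interference does not conflict: the sentence names no form and the list adds one. The sentence's VAS wording and the list's 0-10 rating probably describe the same item. At 6 months, 0 of 2 measures conflict. The conflict therefore touches 2 of 3 time points. No text calls for a comparison of function between arms at enrollment, which leaves 6 weeks as the one follow-up time point exposed.

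**Which statement carries more weight.** The form of the function measure is named three times: short form twice, CAT once. The two short-form entries are in the section whose purpose is to itemise the measures. The CAT entry is in a compressed sentence that also abbreviates the fingers, omits the form for pain interference and describes the pain rating loosely. The simplest reading is one uncorrected word. This is an inference, because no rule of precedence is written down.

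**Effect on the comparison between arms.** Both statements apply to every participant regardless of allocation, and allocation is double-blind. Whichever form is loaded, both arms complete it, and a rank test on its scores is valid. No arm-related bias arises.

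**Effect on the sample size.** The plan's 134 can be reproduced from its inputs in Biostatistical Analyses: effect size 0.50, two-sided alpha 0.05, power 80%. Equal allocation is assumed here because no ratio is stated.

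- Two-sample t-test: 63.77 per arm.
- Divide by the asymptotic relative efficiency of the Wilcoxon-Mann-Whitney test, 3/π = 0.955: 63.77 / 0.955 = 66.8.
- Round up to 67 per arm: 2 × 67 = 134, the stated figure.

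The effect size is standardized, so no property of either form enters the calculation. Choosing CAT or short form leaves 134 unchanged.

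**Effect on power or precision for function.** This cannot be computed. The documents give no score distribution for either form and do not say which is loaded.

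**The case for a change.** The strongest case for acting is that the contradiction is plain. Both statements are current Version 4 text, and neither a broken table nor a redaction explains the difference. CAT is a specific term, harder to dismiss as loose wording than VAS in the same sentence. Inferring the short form from two mentions against one is reasonable, but it is not a stated rule, and correcting the text would cost one clause.

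All of that stands as a description of the text. It does not show a consequence. Two function scores per patient would arise only if both forms were administered, and nothing in the documents suggests that. Mixing forms between patients is equally unsupported. The adherence point has some force, but the monitoring text assigns duties in general terms and does not mention instruments. The low cost of an edit does not create a gain: it would only make the text agree with whatever form REDCap already holds.

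**Conclusion.** The inconsistency is genuine and clerical, and no change to the plan is needed. It comes down to one word in a summary sentence about a secondary outcome. The exposed follow-up results are the 6-week comparison of function between arms and any analysis of factors associated with function that uses the 6-week scores. The 6-month function measure is named once and unambiguously, and the plan ties that contact to one of the secondary hypotheses. The primary outcome, the sample size of 134 and the validity of the comparison between arms are untouched.

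An analyst will see from the REDCap export which form was completed, analyse that score and name the form in the report.

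The conclusion rests on two assumptions: that one form is loaded for enrollment and 6 weeks, and that it is the same for all participants. The documents do not confirm either, but the single REDCap platform and blinded allocation make both reasonable, and nothing in the text points the other way.
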